8.6.6.2 Disease-specific Survival (DSS)

DSS will be computed as

$$\text{DSS (Months)} = (\text{Date of event/censor} - \text{Date of cryoprocedure} + 1) / 30.4375.$$

For each patient that has not died due to kidney cancer, DSS will be censored at the date of death due to other causes or at the date last known to be alive as recorded on the eCRF.

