8.5. Analyses

Continuous variables (e.g., age) will be summarized by the number of subjects, mean, standard deviation, median, interquartile range, minimum and maximum. Categorical variables (e.g., race) will be summarized by frequencies and percentages of subjects in each category.

Reporting from the database may occur at 6 months and then on an annual basis or more frequently as determined.

Lesion size

Lesion size reduction will be determined by examining the change from baseline at follow-up visits. Method of post-treatment imaging including ultrasound, CT or MRI, use of contrast, enhancement and other imaging parameters will be reported for baseline and follow-up visits.

Renal function status

Renal function status will be determined by examining the estimated Glomerular Filtration Rate (eGFR) at baseline and follow-up visits. The estimated Glomerular Filtration Rate will be calculated using the Modification of Diet in Renal Disease (MDRD) formula.⁵

For creatinine in mg/dL:

$$\text{eGFR} = 175 \times \text{Serum Creatinine}^{-1.154} \times \text{Age}^{-0.203} \times [1.212 \text{ if Black}] \times [0.742 \text{ if Female}]$$

Disease recurrence or progression

Disease recurrence or progression will be determined locally by evidence of an increase in lesion size, contrast enhancement, and/or biopsy.

Disease-specific survival rate is defined as the time in days from cryoprocedure to death due to kidney cancer. Subjects who are alive will be censored at date of their last visit. Subjects who have died from causes other than kidney cancer will be censored at the time of death. Disease-specific survival rates will be summarized by using Kaplan-Meier methodology.

Overall survival rate is defined as the time in days from cryoprocedure to death. Subjects who are alive will be censored at the date of the last visit. Overall survival rates will be summarized by using Kaplan-Meier methodology.

Time to recurrence is defined as the time in days from cryoprocedure to disease recurrence or progression. Subjects without disease recurrence or progression will be censored at the date of their last visit or their date of death (due to any cause). Recurrence free survival rates will be summarized by using Kaplan-Meier methodology.

Intra-operative Data

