8.6.6 Analysis of Time-to-Event Endpoints

Rates will be derived from the Kaplan-Meier estimates; 6, 12, 24, 36, 48 and 60 month rates will be presented, together with 95% CIs computed using the log-log transformation methodology of Kalbfleisch and Prentice (1980). Quartiles will be presented and 95% CIs will be calculated on the quartiles using the methodology of Brookmeyer and Crowley (1982) using the log-log standard error. Plots of the Kaplan-Meier curve will be provided showing the number of patients at risk at the date of treatment (i.e., 0 months), and at 6, 12, 24, 36, 48 and 60 months after treatment.

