8.6.6.1 Time to Recurrence (TTR)

TTR will be computed as

$$\text{TTR (Months)} = (\text{Date of event/censor} - \text{Date of cryoprocedure} + 1) / 30.4375.$$

Censoring will be performed in the following order:

- 1) If a patient does not have a baseline lesion assessment, then the TTR time will be censored at the date of cryoprocedure, regardless of whether or not recurrence was observed after treatment.
- 2) If a patient has recurrence but has two or more missing lesion assessment visits (according to the 6 to 60 month analysis visits in Section 6.2.2) immediately before recurrence was observed, the TTR time will be censored at the date of the post treatment lesion assessment that occurred immediately before the first of the missed visits. For example, if a patient had a lesion assessment at Month 6, but did not have an assessment at Months 12 and 24, and then had recurrence at the Month 36 assessment, then the TTR time would be censored at the date of the Month 6 assessment.
- 3) If a patient is known not to have recurrence, the TTR time will be censored at the last date of lesion assessment date, or at the date of cryoprocedure if the patient does not have any post-treatment lesion assessments.

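### Kaplan-Meier rates for disease-specific survival and time to recurrence censor competing deaths: label them as net quantities and add cumulative incidence

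*SAP*

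**What the plan says.** **DSS.** The two documents agree. Protocol section 8.5: "Subjects who have died from causes other than kidney cancer will be censored at the time of death". SAP section 8.6.6.2 keeps that rule: "DSS will be censored at the date of death due to other causes or at the date last known to be alive". It puts death from another cause on the same footing as being last known alive.

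**TTR.** Protocol section 8.5 names death: patients without an event "will be censored at the date of their last visit or their date of death (due to any cause"). SAP section 8.6.6.1 has no rule that mentions death. Its third rule reads "If a patient is known not to have recurrence, the TTR time will be censored at the last date of lesion assessment date", so a patient who dies without recurrence is censored at the last scan before death.

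**TTR, second rule.** If recurrence is found after two or more missed assessment visits, "the TTR time will be censored at the date of the post treatment lesion assessment that occurred immediately before the first of the missed visits". That recurrence is then not an event.

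**Estimator.** SAP section 8.6.6: "Rates will be derived from the Kaplan-Meier estimates; 6, 12, 24, 36, 48 and 60 month rates will be presented". The LIFETEST call in SAP Appendix 2 has one event type, and every patient without it is censored. Protocol section 8.5 calls the TTR output recurrence free survival rates. Neither document plans a cumulative incidence estimate or says that a net quantity is intended.

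**The concern.** A patient who has died of something else can no longer have a recurrence or die of kidney cancer. Censoring removes that patient from the risk set and lets the patients still under observation stand in for what would have happened later. The resulting curve describes a setting in which other deaths do not occur. That is a legitimate quantity, but it is not the share of treated patients who have the event.

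The registry's primary objective is to describe short- and long-term outcomes after cryoablation over five years. Readers of such a report will want to know what fraction of patients recurred, and what fraction died of kidney cancer, by year 5. If they take one minus the planned rate as the answer, the figure will be too high whenever other-cause deaths occur and nothing else disturbs it. The protocol's label for the TTR curve invites a second misreading: that the curve gives the share alive and free of recurrence.

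**Working it through.** **Inputs.** From the documents: the censoring rules above, 5 years of follow-up and about 250 patients (SAP sections 4.1 and 4.4). The documents state no recurrence, kidney-cancer death or other-cause death rate, so there is no planned figure to reproduce. All rates below are assumptions.

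**Direction.** Let H1 be the cumulative cause-specific hazard of the event and H2 that of the competing death.
- One minus Kaplan-Meier estimates 1 − exp(−H1), which is the integral of exp(−H1) dH1.
- The actual probability (cumulative incidence) is the integral of exp(−H1 − H2) dH1.

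The second integrand is never larger than the first, so the complement is at least as large as the actual probability. This does not depend on constant hazards.

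**Size.** With constant yearly rates r (event) and d (competing death), at 5 years:
- 1 − KM = 1 − exp(−5r)
- Cumulative incidence = r/(r+d) × [1 − exp(−5(r+d))]

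For example, with r = 0.02 and d = 0.03: 1 − exp(−0.10) = 9.5%, against 0.4 × (1 − exp(−0.25)) = 0.4 × 0.2212 = 8.8%.

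| Event | d per year | 1 − KM | Cumulative incidence | Gap (points) |
|---|---|---|---|---|
| Recurrence, r = 2% | 3% | 9.5% | 8.8% | 0.7 |
| | 5% | 9.5% | 8.4% | 1.1 |
| | 8% | 9.5% | 7.9% | 1.6 |
| Kidney-cancer death, r = 0.5% | 3% | 2.5% | 2.3% | 0.2 |
| | 5% | 2.5% | 2.2% | 0.3 |
| | 8% | 2.5% | 2.0% | 0.4 |

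Gaps are taken before rounding. In relative terms they run from about 8% to 21%.

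**Against precision.** The 95% half-width with 250 patients and no censoring is 1.96 × √(p(1−p)/250): 3.7 points at p = 10% and 2.1 points at p = 3%. Every gap above is smaller. A larger sample would narrow the interval but not the gap.

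**The label.** On the same recurrence assumptions the Kaplan-Meier event-free rate is exp(−0.10) = 90.5%. The share who have not recurred, dead or alive, is 100% minus the cumulative incidence: 91.2%, 91.6% or 92.1%. The share alive and recurrence-free is exp(−5(r+d)): 77.9%, 70.5% or 60.7%. The curve called recurrence free survival is neither.

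**Second TTR rule.** I simulated 200,000 patients per row with a net 5-year recurrence risk of 10% and 5-year other-cause mortality of 20%. Scans were at 6, 12, 24, 36, 48 and 60 months, each missed independently. Patients without an observed recurrence were censored at their last scan.

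| Visits missed | Actual probability | 1 − KM without rule 2 | 1 − KM with rule 2 | Observed recurrences discarded |
|---|---|---|---|---|
| 0% | 9.0% | 10.0% | 10.0% | 0% |
| 20% | 9.0% | 10.2% | 9.5% | 7% |
| 35% | 9.0% | 10.5% | 8.5% | 19% |
| 50% | 8.9% | 11.1% | 7.0% | 36% |

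Rule 2 pulls the figure down and, at 35% missed, takes it below the actual probability. The two effects roughly cancel at 20% missed when other-cause mortality is 10%, and at 35% missed when it is 30%. DSS is not affected by this rule.

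**The case against.** Much of the case for leaving the plan alone is sound.

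- **DSS is conventional.** Censoring other-cause deaths is a standard definition, and it was set in the protocol before the SAP. A reader might infer that the DSS analysis is wrong. The documents do not support that: what is missing is a label and a companion estimate.
- **The plan does not present observed risks.** A reader might infer that the 6- to 60-month rates are offered as the share of patients with the event. The documents plan event-free rates and nowhere plan one minus Kaplan-Meier. The overstatement arises when a reader inverts the rate.
- **An unconditional overstatement of recurrence is not established.** Rule 2 works the other way. Visits follow each physician's standard of care, so missed windows are plausible.
- **No mortality is given.** A reader might infer from the 75-and-over age band and the comorbidity tables that other-cause deaths will outnumber kidney-cancer deaths. Those are tabulation categories, not rates.
- **Partial disclosure exists.** SAP section 8.1 tabulates reasons for censoring, section 8.6.4 gives recurrence percentages by visit, and section 8.6.6.3 reports overall survival.

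These outputs lower the risk of misreading, but none of them gives a cumulative probability of recurrence or of kidney-cancer death. For a descriptive five-year registry that gap remains.

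**Conclusion.** The point holds as one of labelling and completeness. The Kaplan-Meier rates for DSS and TTR are net of other deaths, neither document says so, and no planned output gives the actual risk. For DSS the complement of the rate overstates that risk by about 0.2 to 0.4 points under the assumed rates. For TTR, competing deaths alone contribute about 0.7 to 1.6 points, but the direction of the reported figure depends on how many visits are missed. All sizes rest on assumed constant rates, and the second-rule check also assumes visits missed at random. The effect is small beside sampling error in about 250 patients. It is still worth correcting, because it is systematic and the remedy is cheap.

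**What to change.** 1. Keep all planned Kaplan-Meier output. In SAP section 8.6.6 and in table titles, state that the DSS and TTR rates are net (cause-specific), with deaths censored. Do not carry the protocol's recurrence free survival label into the report without that qualification.
2. Add Aalen-Johansen cumulative incidence with 95% confidence intervals at 6, 12, 24, 36, 48 and 60 months. For kidney-cancer death, the competing event is death from other causes. For recurrence, it is death from any cause without recorded recurrence.
3. Quote these as the 5-year risks. For recurrence, also report how many events rule 2 removed, because cumulative incidence does not restore them.

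**Cost.** The status variable needs a further code for competing death, and there is one extra table. Cause of death is already reviewed for DSS (SAP section 6.4.5), and death dates are already needed for overall survival. TTR needs a small new derivation that uses the death date, with a stated rule for deaths long after the last lesion assessment. The report will have two sets of figures to explain. The Cox models need no change.

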8.6.6.3 Overall survival

OS will be computed as

$$\text{OS (Months)} = (\text{Date of death/censor} - \text{Date of cryoprocedure} + 1) / 30.4375.$$

For each patient that has not known to have died, OS will be censored at the date last known to be alive as recorded on the eCRF.

8.6.7 Analysis of Quality of Life Questionnaire (SF-12)

Change from baseline and percentage change from baseline for the ten SF-12 scores listed in Section 6.4.7 will be separately summarized for the 6 and 12 month timepoints by descriptive statistics. The analysis will also be performed separately by laparoscopic and percutaneous procedure methods.

8.6.8 Development of metastatic disease

The number and percentage of patients who developed metastatic disease will be given. A 95% CI for the percentage will be computed using the method of Wilson (1927).

The duration (months) between date of cryoprocedure and date of development of metastatic disease will be computed as

$$(\text{Date of development of metastatic disease} - \text{Date of cryoprocedure} + 1) / 30.4375,$$

and will be summarized with descriptive statistics.

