8.2. Missing Data

As TRACE is an observational registry of subjects and does not strictly define post-cryoablation subject follow-up, the frequency, volume and extent of data collected for each enrolled subject will vary. Missing data will not be imputed.

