4.4 Determination of Sample Size

Approximately 250 patients are expected to participate in TRACE. As the registry is an observational, non-comparative study, power calculations have not been performed. The estimated sample size has been established to help ensure an adequate population of “completed patients,” defined as those patients completing four or more years of follow-up, at the closure of the registry. This study is not powered for formal statistical analysis.

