6.4.8 Development of metastatic disease

The endpoint of interest to assess the development of metastatic disease is the “Yes” or “No” response to the question “Is there evidence of metastatic disease?” in the follow-up eCRF page. Per the Steering Committee, metastatic disease is limited to metastases to or from the kidney.

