8.3 Analysis Populations

8.3.1 Intent To Treat (ITT) Population

All patients where a cryoprocedure was attempted with a Galil Medical Cryoablation System and needles and who met the study eligibility criteria will form the Intent-to-Treat (ITT) population. This population will be used for the analysis of all efficacy and safety data. Patients in the ITT population will be identified as follows:

- 1) First include all patients with a date of cryotherapy recorded
- 2) Then exclude any patients who have been manually identified as having not met all eligibility criteria from a review of monitoring reports.

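### Metastatic disease is reported as a crude percentage with no time horizon, stated denominator or handling of early exit, so the figure depends on how long patients were followed

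*SAP*

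**What the plan says.** SAP 6.4.8 takes the endpoint from a yes/no item on the follow-up eCRF page and adds that "metastatic disease is limited to metastases to or from the kidney". For the analysis, SAP 8.6.8 states: "The number and percentage of patients who developed metastatic disease will be given". A Wilson 95% CI accompanies the percentage. The same section continues: "The duration (months) between date of cryoprocedure and date of development of metastatic disease will be computed", and that duration is summarised descriptively.

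Section 8.6.8 names no time point, denominator or censoring rule. The denominator has to be inferred from SAP 8.3.1, which says of the ITT population: "This population will be used for the analysis of all efficacy and safety data". SAP 8.3.2 also uses the RCC population for efficacy.

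Other parts of the plan do address time under observation:

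- SAP 8.6.6 gives Kaplan-Meier rates from 6 to 60 months for time to recurrence (TTR), disease-specific survival (DSS) and overall survival (OS).
- SAP 8.6.4 bases its by-visit percentages on patients still in follow-up.

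Neither rule is carried into 8.6.8.

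**The concern.** The documents themselves expect unequal observation. Protocol 8.2 says "the frequency, volume and extent of data collected for each enrolled subject will vary" and rules out imputation. SAP 4.1 plans five years per patient on schedules set by local practice. Protocol 8.1 and SAP 4.4 count a patient as completed from four years. SAP 8.1 lists withdrawn consent and loss to follow-up among the reasons for discontinuation, and SAP 7.3 does not replace dropouts.

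Under 8.6.8 as written, a patient lost at month 6 without metastasis counts the same as one observed free of metastasis to month 60. Other things equal, more loss lowers the percentage, so weaker follow-up can look like better disease control. The summary of months to metastasis leaves out everyone whose event had not occurred by the end of observation. It is therefore tilted towards early times and conveys no risk.

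The primary objective is short- and long-term outcomes, and metastasis is a listed efficacy endpoint. Its figure would appear in the same report as 60-month rates but on a different, undefined time base.

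**Working it through.** **Is there a figure to reproduce?** No. The documents state no metastasis rate, loss rate or expected event count. The only size given is "Approximately 250 patients are expected to participate in TRACE", with no calculation behind it. All rates below are assumptions, chosen to show direction and range.

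**Model.** Constant hazards per year: l for metastasis, m for death without metastasis, c for loss to follow-up. Observation stops at T years.

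- True cumulative incidence at 5 years: F = l/(l+m) × (1 − exp(−5(l+m)))
- Expected crude proportion: l/(l+m+c) × (1 − exp(−T(l+m+c)))

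**Worked case.** Take F = 5% and m = 0.03.

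1. Solving for l gives about 0.01106. Check: 0.01106/0.04106 × (1 − exp(−0.2053)) = 0.2694 × 0.1856 = 0.050.
2. With c = 0.10 and T = 5, the crude proportion is 0.01106/0.14106 × (1 − exp(−0.7053)) = 0.0784 × 0.5060 = 0.0397.
3. The ratio to truth is 0.0397/0.05 = 0.79.

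**Range.** True risks of 2%, 5% and 10%, with death hazards of 0, 0.03 and 0.05 per year:

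| Loss hazard per year | 1 − exp(−5c) | Crude / true 5-year risk |
|---|---|---|
| 0 | 0% | 1.00 |
| 0.05 | 22% | 0.89 (0.885 to 0.892) |
| 0.10 | 39% | 0.79 (0.788 to 0.799) |
| 0.15 | 53% | 0.71 (0.704 to 0.720) |
| 0.20 | 63% | 0.64 (0.633 to 0.651) |

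The ratio depends almost entirely on loss. Deaths kept in the denominator cause no bias in a cumulative incidence.

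**Short follow-up without loss.** If every patient were followed for exactly four years, the true 5% (m = 0.03) would appear as 0.2694 × (1 − exp(−0.1642)) = 4.1%.

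**Late events.** SAP 6.2.2 has a 60 Month window running to 66 months and a Post 60 Month window, and 8.6.8 sets no cut-off. For the same true 5%:

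| Loss hazard per year | Crude, follow-up to 5.5 years | Crude, follow-up to 7 years |
|---|---|---|
| 0 | 5.4% | 6.7% |
| 0.05 | 4.8% | 5.7% |
| 0.10 | 4.2% | 4.9% |

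**Interval and alternative estimator.** Simulation with N = 250, 2,000 runs, m = 0.03 and T = 5. Coverage is of the true 5-year risk by the nominal 95% Wilson interval:

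| True risk | Loss hazard per year | Mean crude | Mean Aalen-Johansen | Wilson coverage |
|---|---|---|---|---|
| 5% | 0 | 5.0% | 5.0% | 96% |
| 5% | 0.05 | 4.5% | 5.0% | 96% |
| 5% | 0.10 | 4.0% | 5.0% | 93% |
| 5% | 0.15 | 3.6% | 5.0% | 88% |
| 10% | 0 | 10.0% | 10.0% | 96% |
| 10% | 0.05 | 8.9% | 10.0% | 93% |
| 10% | 0.10 | 7.9% | 10.0% | 84% |
| 10% | 0.15 | 7.2% | 10.1% | 71% |

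**Kaplan-Meier with deaths censored.** This targets 1 − exp(−5l). For a true 5% it gives 5.4% at m = 0.03 and 5.6% at m = 0.05, so it overstates the cumulative incidence.

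**The case against.** The strongest reply is that the SAP never presents this percentage as a 5-year risk. It is a descriptive count in a registry with no power calculation. SAP 8.1 reports duration of follow-up, numbers followed to each time point up to 60 months, and reasons for discontinuation, so a reader can see how complete observation was. Protocol 8.5 promised Kaplan-Meier only for TTR, DSS and OS, so the SAP breaks no commitment. By-visit percentages and Wilson intervals are also used for other lesion endpoints (SAP 8.6.4 and 8.6.9.1). All of this stands. It makes the problem one of interpretation, but it does not supply the missing horizon or denominator, and the disposition tables cannot turn a crude percentage into a risk.

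A reader might infer two stronger points that the documents do not support:

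- **That the figure necessarily understates the 5-year risk.** Understatement is likely under material loss. It vanishes with no loss, and events after 60 months could cancel or reverse it.
- **That the Wilson interval is invalid because it assumes equal follow-up.** With independent patients, metastasis recorded or not is still a yes/no outcome, and the interval is valid for that proportion. It simply targets a different quantity. At a true 5% and N = 250, it still covers the 5-year risk 93% of the time at a loss hazard of 0.10. For example, 10/250 = 4.0% has an interval of 2.2% to 7.2%.

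**Conclusion.** The point holds as a gap in specification. Following 8.6.8 as written gives a percentage whose value depends on how long patients happened to be followed, and a time summary that can only cover those with the event. Neither can be compared with the 60-month rates for TTR, DSS and OS.

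If events are counted only to five years, the crude figure is about 0.89 to 0.64 of the true 5-year risk at loss hazards of 0.05 to 0.20 per year. This rests on constant hazards, on loss unrelated to metastasis risk, and on the ITT or RCC population as denominator, which 8.6.8 does not state. The actual size cannot be fixed from the documents and would be small if loss is low. The change is worth making, but the crude count is not wrong as a description.

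**What to change.** In SAP 8.6.8, add the cumulative incidence of first metastasis by the Aalen-Johansen method:

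- death without metastasis as a competing event
- estimates with 95% CIs at 12, 24, 36, 48 and 60 months
- ITT and RCC populations
- censoring at the last follow-up at which the metastasis item was answered

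Do not simply extend the Kaplan-Meier method of 8.6.6 with deaths censored, because that overstates the risk. Keep the count and crude percentage with its Wilson interval as description only, and state its denominator.

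The cost is one more table. It should need no new data collection, since 8.6.8 already uses the metastasis date and 6.4.8 the yes/no item. The downsides are wide intervals if events are few and possibly a less favourable figure.
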